2. SYNOPSIS

Name of Sponsor/ Company: Alkermes, Inc	
Name of Study Drug: ALKS 5461	
Name of Active Ingredients: buprenorphine (BUP) and samidorphan	
Title of Study: A Phase 3 Multicenter Study of the Long-term Safety and Tolerability of ALKS 5461 for the Adjunctive Treatment of Major Depressive Disorder in Adults who Have an Inadequate Response to Antidepressant Therapy (the FORWARD-2 Study)	
Investigators: This will be a multicenter, multinational study.	
Study Period: First subject consented: Q2 2014 Last subject completed: 2017	Phase of development: 3
Objective: 
 To assess the long-term safety and tolerability of ALKS 5461 for use as an adjunctive therapy to antidepressants for the treatment of major depressive disorder (MDD) 	
Methodology: 
ALKS 5461 is a fixed-dose combination product consisting of BUP and samidorphan in a 1:1 (weight/weight) ratio. Throughout this protocol ALKS 5461 dose levels will be referred to as dose of BUP/samidorphan expressed as weight in mg (eg, a 2 mg BUP:2 mg samidorphan dose will be expressed as ALKS 5461 2/2).
 
This study will evaluate the safety and tolerability, and explore the treatment effect of ALKS 5461 administered for 52 weeks as an adjunctive therapy to antidepressants for the treatment of MDD in subjects who have had 1 to 2 inadequate responses to an approved antidepressant therapy (ADT). Subjects will have been treated with an adequate dose of an approved ADT for at least 8 weeks, with a stable dose over the last 4 weeks prior to study entry. An adequate dose is defined as a dose that is greater than or equal to the minimum effective dose on the Massachusetts General Hospital Antidepressant Treatment Response Questionnaire (ATRQ), inclusive of up to 3 weeks for titration into the adequate dose range.
 
Subjects will enter into the study in one of the following 3 ways, based on their previous experience with ALKS 5461:
 
 New Subjects: those who have not been randomized in a prior study of ALKS 5461 within 2 years Continuing Subjects: those who have completed the treatment period of study ALK5461-205, ALK5461-206, ALK5461-207, or ALK5461-210 within the past 10 days Lead-in Subjects: those who participated in study ALK5461-205, ALK5461-206, or ALK5461-207 within the past 10 days, and met the criteria for response to ADT during the prospective lead-in (PLI) period of that antecedent study, but did not meet the criteria for 	

remission

All New Subjects will be initially evaluated for eligibility at screening (Visit 1), to occur up to 28 days prior to Visit 2. Continuing Subjects and Lead-in Subjects will not have a separate screening visit and will begin participation in this study at Visit 2.

At Visit 2, all eligible, consenting subjects will begin the treatment period. Subjects who are not receiving ALKS 5461 at study entry will require a 1-week titration period. Subjects entering the study already receiving ALKS 5461 will not require a titration period. To maintain the blinded dosing scheme in ALK5461-206 and ALK5461-207, Continuing Subjects from those studies will be blinded to whether or not they receive a 1-week titration.

Starting on Day 8 (Visit 3), the target dose for the remaining 51 weeks for all participating subjects will be ALKS 5461 2/2. Attempts should be made to achieve and maintain the ALKS 5461 2/2 dose throughout that period, if it is tolerated. However, flexible down-titration to ALKS 5461 1/1 or 0.5/0.5 is permitted at the investigator's discretion, if tolerability issues persist. Once a subject has stabilized after down-titration, attempts should again be made to achieve and maintain the target dose of ALKS 5461 2/2 over the course of treatment, dependent on the individual subject's experience with study drug tolerability.

Dose adjustment of ADT during the treatment period is permitted for optimal therapeutic effect within the recommended dose range, however ADT dose adjustment should not be made within the same week as ALKS 5461 dose adjustment. Furthermore, subjects are not permitted to change ADTs during the course of the study period.

During the 52-week treatment period, subjects will return to the clinic for periodic scheduled visits (Visits 2-14) at which safety, tolerability, and treatment effect over time will be assessed.

A 4-week safety follow-up period will occur following the ALKS 5461 treatment period. During the 4-week follow-up period, there are a total of 4 clinic visits (Visits 15-18), as well as 7 safety assessments by phone. The clinic visits will occur 1 day, 1 week, 2 weeks, and 4 weeks following the end of treatment visit (Visit 14). The phone assessments will occur daily for the first week between visits, and weekly during the second and third week.

If any adverse events (AEs) are reported that relate to opioid withdrawal (eg, nausea, vomiting, restlessness, hyperhidrosis) during a phone assessment in the follow-up period, the subject will be asked to come into the clinic as soon as possible to receive a Clinical Opiate Withdrawal Scale (COWS) assessment.

Number of Subjects (planned):

It is estimated that approximately 1,500 subjects will be enrolled in this study.

Main Criteria for Inclusion:

The main criteria for study eligibility are as follows:

- New Subjects must have a Diagnostic and Statistical Manual of Mental Disorders, 4th Edition, Text Revision (DSM-IV-TR) MDD diagnosis and an inadequate response to current approved ADT. They will not have participated in a prior trial of ALKS 5461 within 2 years.
- Continuing Subjects must have completed the treatment period of ALK5461-205, ALK5461-206, ALK5461-207, or ALK5461-210 within 10 days of the baseline visit for this study.
- Lead-in Subjects must have completed the PLI period of ALK5461-205, ALK5461-206, or ALK5461-207 within 10 days of the baseline visit for this study and met the criteria for response to ADT during the PLI, but not for remission.

Study Drug, Dosage, Duration, and Mode of Administration:

ALKS 5461 consists of buprenorphine (BUP), a United States Drug Enforcement Administration (US DEA) Schedule III narcotic, and samidorphan, a US DEA Schedule II controlled substance.

The following doses will be used in the study:

- ALKS 5461 0.5/0.5 (0.5 mg BUP:0.5 mg samidorphan)
- ALKS 5461 1/1 (1 mg BUP:1 mg samidorphan)
- ALKS 5461 2/2 (2 mg BUP:2 mg samidorphan)

Tablets will be administered sublingually, daily for up to 52 weeks.

Reference Therapy, Dosage, Duration and Mode of Administration:

This safety study has no reference therapy.

Study and Treatment Duration:

For New Subjects, the study duration will be up to 60 weeks, which includes up to 4 weeks for the screening period, 52 weeks for the dosing period, and 4 weeks for the follow-up period.

For Continuing Subjects and Lead-in Subjects, the study duration will be up to 56 weeks, which includes 52 weeks for the dosing period, and 4 weeks for the follow-up period.

Criteria for Evaluation:

Safety and Tolerability:

The following assessments will be collected to evaluate safety and tolerability throughout the study:

- AEs
- clinical laboratory tests (chemistry, hematology, and urinalysis)
- vital signs
- body weight
- electrocardiogram (ECG)
- Columbia Suicide Severity Rating Scale (C-SSRS)
- COWS

Efficacy: The following assessments will be made for exploratory evaluation of treatment effect over time:

- Montgomery-Åsberg Depression Rating Scale (MADRS)
- Hamilton Rating Scale for Anxiety (HAM-A)
- Clinical Global Impression – Severity (CGI-S)

Pharmacokinetics:

Plasma samples will be collected at specified time points from consenting subjects enrolled in the US only. These samples will be used to quantify concentrations of BUP, samidorphan, and relevant metabolites. Concentrations of background ADTs that subjects report taking during the study may be quantified, as appropriate.

Statistical Methods:

Safety: Safety and tolerability analyses will be performed using data from the safety population, defined as all subjects who receive at least 1 dose of ALKS 5461. Reported AE terms will be coded using the Medical Dictionary for Regulatory Activities (MedDRA®) preferred terms and system organ class categories.

Safety assessments will be summarized using descriptive statistics along with supportive listings.

Efficacy: Exploratory evaluation of treatment effect over time will be performed using data from the full analysis set (FAS), defined as all subjects who receive at least 1 dose of ALKS 5461 and complete at least 1 post-baseline efficacy assessment (MADRS).

Pharmacokinetics:

Plasma concentration data for BUP, samidorphan, and relevant metabolites as well as background ADTs will be listed and summarized. Additionally, concentration data obtained from this study may be combined with data from other studies for population PK analysis, which will be reported separately.

Sample Size Considerations:

It is estimated that approximately 1,500 subjects will be enrolled in order to ensure that a minimum of 100 subjects achieve 12 months of exposure to ALKS 5461 and a minimum of 300 subjects achieve 6 months of exposure.

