7.1.2. New Subjects

In order to qualify for participation in this study, in addition to meeting the criteria for all subjects presented in Section 7.1.1, New Subjects must also meet all of the following criteria:

5. Be between 18 and 70 years of age, inclusive
6. Have a body mass index (BMI) 18.0 - 40.0 kg/m²
7. Have not been randomized in a prior study of ALKS 5461 within 2 years
8. Have a Diagnostic and Statistical Manual of Mental Disorders, Fourth Edition, Text Revision (DSM-IV-TR) MDD diagnosis at screening, as assessed and confirmed by the Mini International Neuropsychiatric Interview (MINI) administered by qualified site staff. The diagnosis of MDD must be considered by the investigator as the primary source of current distress and functional impairment
9. Have a current major depressive episode (MDE) lasting 8 weeks to 24 months
10. Have been treated with an adequate dose of an approved ADT during the current MDE for at least 8 weeks, with the same, adequate dose over the last 4 weeks, which is expected to remain stable throughout the study
11. Have an inadequate response to current ADT and up to 1 prior ADT during the current MDE. An inadequate response is defined as less than a 50% reduction in depressive symptom severity during a course of treatment at least 8 weeks in duration with an adequate dose of an approved ADT, as assessed on-site using the Massachusetts General Hospital Antidepressant Treatment Questionnaire (ATRQ)

(NOTE: If a subject had an adequate response to an ADT in the past, but now has relapsed on the same ADT at the same or lower dose and is experiencing a new MDE, this would not represent an adequate trial of an ADT for this new MDE)

12. Have a HAM-D total score of ≥ 14 at Visit 1 and ≥ 10 at Visit 2

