8.4.2. Concomitant and Prohibited Medications

8.4.2.1. Concomitant Medications

All medications taken by a given subject within 30 days of screening through follow-up will be recorded as detailed in [Section 8.3.10](#). The concomitant medication review on each visit will include all prescription medications including ADT, OTC medications, and vitamins and dietary supplements. Concomitant medications will be reviewed at all clinic visits and all phone assessments.

Subjects will be permitted to continue taking concomitant medications during the study provided that these medications are not prohibited (see [Sections 7.2](#) and [8.4.2.2](#)). The investigator may discontinue or adjust the dose of any of these concomitant medications to ensure subject safety. At the investigator's discretion, new concomitant medications may be administered during the course of the study for the treatment of an AE or a change in disease state. If a prohibited medication is needed, the investigator should notify the medical monitor as soon as possible to discuss the continued participation of the subject in the study.

Dose adjustment of approved ADT during the treatment period is permitted for optimal therapeutic effect within the recommended dose range, however ADT dose adjustment should not be made within the same week as ALKS 5461 dose adjustment. Further, subjects are not permitted to change ADTs during the course of the study period.

See [Section 9.5](#) for complete details of ALKS 5461 dose adjustments.

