9.5. Study Drug Dose Adjustment and Stopping Rules

Starting on Day 8 (Visit 3), attempts should be made to achieve and maintain the target dose of ALKS 5461 2/2 over the course of treatment, if tolerated. However, at any time during the study, flexible down-titration to ALKS 5461 1/1 and then to ALKS 5461 0.5/0.5 is permitted at the investigator's discretion, if tolerability issues persist. Once a subject has stabilized after down-titration, attempts should again be made to achieve and maintain the target dose of ALKS 5461 2/2 over the course of treatment, dependent on the individual subject's experience with study drug tolerability.

Dose adjustment of approved ADT during the treatment period is permitted for optimal therapeutic effect within the recommended approved dose range, however ADT dose adjustment should not be made within the same week as ALKS 5461 dose adjustment. Furthermore, subjects are not permitted to change ADTs during the course of the study period.

The study may be stopped at any time or study sites may be closed at the sponsor's discretion.

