3.5. Treatment Adherence Rate and Extent of Exposure

Treatment adherence to the daily dosing schedule of study drug is measured as the rate of actual compared to intended number of doses to be taken during the ALK5461-208 study. Percentage of treatment adherence will be calculated during 52-week treatment period for the Safety Population as follows:

 $\frac{\text{Total tablets taken}}{\text{Total tablets subject should have taken from the first dose date to the last dose date, inclusive}}$

Duration of exposure to study drug is defined as the number of days from the first dose date of study drug taken to the date of the last dose taken during the ALK5461-208 study, inclusive.

Treatment adherence and exposure of study drug will be summarized by prior ALKS 5461 exposure and overall for the Safety Population.

Treatment adherence will be summarized as a continuous measure using descriptive statistics (number of subjects, mean, SD, median, minimum, and maximum) and as a categorical measure using the number and percentage of subjects in each adherence rate category (rounded to the whole number): <70%; $\ge70\%$ to 80%; >80% to 90%; >90% to 100%; >100% to 110%; >110% to 119%; and $\ge120\%$.

The number of subjects exposed to study drug and the average days of treatment will be summarized as a continuous measure using descriptive statistics (number of subjects, mean, SD, median, minimum, and maximum).

The exposure to ADT will be summarized by ADT class (SSRI, SNRI, TCA, MAOI and other) and Preferred Term (ADT name) using descriptive statistics in a similar fashion. In addition, descriptive statistics of mean daily dose of ADT will be summarized by ADT class and Preferred Term.

The descending cumulative exposure of study drug will be categorized as ≥ 1 day, ≥ 1 month, ≥ 3 months, ≥ 6 months, ≥ 9 months and ≥ 12 months, and will be summarized as a categorical measure using the number and percentage of subjects in each category.

The definitions in Table 3 will be used to define cumulative exposure.

Table 3: Definitions to Define Study Drug Cumulative Exposure

	Definition	Programming Derivation
≥ 1 day	≥ 1 day	
≥ 1 month	≥ 23 days (3 weeks)	\geq (365.25/12)-7 days
\geq 3 months	\geq 84 days (12 weeks)	\geq [(365.25/12)x3]-7 days
≥ 6 months	≥ 169 days (24 weeks)	\geq [(365.25/12)x6]-14 days
≥ 9 months	≥ 260 days (37 weeks)	\geq [(365.25/12)x9]-14 days
≥ 12 months	≥ 351 days (50 weeks)	≥ 365.25 -14 days

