3.6.1.3. Examination of Subgroups

No subgroup analysis for efficacy is planned.

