3.6.2. Efficacy Analysis

3.6.2.1. Montgomery-Asberg Depression Rating Scale (MADRS)

The MADRS measures the severity of depressive symptoms and consists of 10 items. The MADRS-10 is the sum of all 10 items and ranges from 0 to 60. The MADRS-6 is the sum of the following 6 items: item 1 reported sadness; item 2 apparent sadness; item 3 inner tension; item 7 lassitude; item 8 inability to feel; and item 9 pessimistic thoughts and ranges from 0 to 36. Section 6.2 describes the handling of MADRS-10 if any of the items of the MADRS is missing.

The following endpoints will be assessed:

- Change from baseline in MADRS-10 and MADRS-6 score
- Proportion of subjects demonstrating MADRS treatment response, defined as a ≥50% reduction in MADRS-10 from baseline
- Proportion of subjects achieving remission, defined as a MADRS-10 of \leq 10

Descriptive summary statistics of baseline MADRS-10 and MADRS-6 score and change from baseline at each visit including the last assessment during treatment period will be provided by prior ALKS 5461 exposure and overall based on observed data. In addition, the figures of MADRS-10 and MADRS-6 score (including standard error), mean change from baseline (including standard error) over time including the last assessment during treatment period will be provided by prior ALKS 5461 exposure and overall based on observed data.

The responder and remission endpoints are derived based on the observed MADRS-10. The number and percentage of subjects demonstrating MADRS-10 treatment response and remission by visit including the last assessment during treatment period will be provided based on FAS. The figures of MADRS-10 responder rate and MADRS-10 remission rate over time including the last assessment during treatment period will be provided by prior ALKS 5461 exposure and overall.

The individual MADRS item scores will not be summarized but will be included in the subject listing.

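### Background antidepressant doses may be changed for therapeutic effect during the 52 weeks, and the SAP's exploratory efficacy summaries do not separate gains that follow an increase

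*Protocol*

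**What the plan says.** The permission appears three times in the protocol:

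- Synopsis, Methodology: "Dose adjustment of ADT during the treatment period is permitted for optimal therapeutic effect within the recommended dose range".
- Section 8.4.2.1: "Dose adjustment of approved ADT during the treatment period is permitted for optimal therapeutic effect within the recommended dose range".
- Section 9.5: "Dose adjustment of approved ADT during the treatment period is permitted for optimal therapeutic effect within the recommended approved dose range".

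Besides the dose range, there are two limits. Section 9.5 says "ADT dose adjustment should not be made within the same week as ALKS 5461 dose adjustment", and subjects may not change to another ADT. Inclusion criterion 10 (Section 7.1.2) admits New Subjects on an adequate ADT dose "which is expected to remain stable throughout the study". The criteria specific to Continuing and Lead-in Subjects (7.1.3, 7.1.4) carry no such wording.

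Protocol Section 11 presents change from baseline in MADRS, HAM-A and CGI-S as an exploratory assessment of the effect of ALKS 5461 over time. SAP 3.6.1 bases all efficacy summaries on observed data. SAP 3.6.2.1 adds: "The responder and remission endpoints are derived based on the observed MADRS-10". SAP 3.6.1.3 says: "No subgroup analysis for efficacy is planned". On ADT dose, SAP 3.5 says that "descriptive statistics of mean daily dose of ADT will be summarized by ADT class and Preferred Term".

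**The concern.** An ADT increase made for therapeutic effect is an active co-treatment aimed at the same symptoms that the efficacy scales measure. With no control arm, nothing in the design absorbs its contribution. A responder or remitter whose ADT dose was raised first looks the same in the tables and figures as one whose ADT dose never changed.

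What is at stake is how the 52-week efficacy curves can be read. The point matters most for Lead-in Subjects. They had already responded to ADT without remitting, and criterion 14 asks for only 5 weeks at the minimally effective dose. A remission after a further ADT increase in this group would be displayed with the others. If increases are more common in one prior-exposure group than in the other, the side-by-side display of those groups is affected too.

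**Working it through.** The plan gives no figure to reproduce, so the check is mainly one of text, followed by arithmetic on assumed values to show scale.

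**1. Is an increase possible in practice?** The protocol's word is adjustment, with no restriction on direction. The minimally adequate doses in the ATRQ (Appendix C) lie well below the Appendix B maxima: 50 against 200 mg for sertraline, 20 against 80 mg for fluoxetine, 60 against 120 mg for duloxetine. Increases are therefore possible; so are decreases.

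**2. Does any efficacy output take account of ADT dose change?**

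- SAP 3.6.2.1 to 3.6.2.3: by-visit and last-assessment summaries of observed scores. No flag, censoring, stratification or sensitivity analysis for ADT change.
- SAP 3.6.1.3: no efficacy subgroups.
- SAP 3.4: ADTs by class and Preferred Term, and a list of subjects taking them. Not linked to scores.
- SAP 3.5: ADT exposure and mean daily dose by class and drug. An average shows neither who had an increase nor when.
- SAP 3.7.2: ADT class is a subgroup for TEAEs only.

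The answer is no. The scores concerned are those from scheduled visits, the early-termination visit mapped forward under SAP 6.1, and the last on-treatment assessment. Unscheduled scores stay out of the by-visit tables (SAP 3.1, 6.1).

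**3. Are the data available?** Yes. Protocol 8.3.10 records name, dose, regimen and start and stop dates of each medication, ADT included. SAP 6.3 has a rule for partial dates.

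**4. Scale, on assumed values only.** Let p be the share of observed subjects with an ADT increase, g the extra MADRS-10 gain it brings in them, and r the extra probability of remission.

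- Shift in mean change = p × g. Low: 0.05 × 2 = 0.1 points. High: 0.30 × 6 = 1.8 points.
- Shift in remission rate = p × r. Low: 0.05 × 0.10 = 0.5 percentage points. High: 0.30 × 0.30 = 9 percentage points.

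None of p, g or r is in the documents.

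**5. Would restricting to scores before the first increase correct the mean?** Assume that 80% of subjects have no increase and average −15 points. Assume that the other 20% would average −5 without an increase and reach −8 with one.

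| Summary | Calculation | Mean change |
|---|---|---|
| Had no one increased | 0.8 × (−15) + 0.2 × (−5) | −13.0 |
| SAP, all observed scores | 0.8 × (−15) + 0.2 × (−8) | −13.6 |
| Pre-increase scores only | the 80% alone | −15.0 |

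The SAP's mean is 0.6 points too favourable and the restricted mean 2.0 points too favourable. If increases go to subjects who are doing poorly, the restriction removes those subjects from later visits and makes matters worse.

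**6. Does counting a subject as not achieved after an increase avoid this?** Yes, for response and remission, if the denominator is kept. No one is dropped. The rate falls by p times the proportion achieving the endpoint among subjects with an increase, so by at most p. It is conservative, because some of them would have achieved it anyway.

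**The case against.** The strongest reply is that this is a safety study. The only objective is safety and tolerability, efficacy is exploratory and descriptive, and no efficacy test is planned. Natural course, regression to the mean and dropout affect the same curves, so dealing with ADT increases would still not isolate a drug effect. All of this stands, and it limits how much the point matters. It does not remove it: natural course cannot be separated in a single arm, whereas ADT change is recorded and can be shown. The SAP already gives disposition for subjects down-titrated on study drug (3.2.2) and TEAE subgroups by ADT class, benzodiazepine use and opioid use (3.7.2).

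It can also be said that subject listings may reveal who changed dose and when. That is possible. The listing shells are in a separate document, and the SAP text does not specify their columns. A listing would in any case not link dose changes to the efficacy summaries.

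A reader might go further than the documents allow in two ways:

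- **That dose adjustment breaches a study-wide rule of ADT stability.** Criterion 10 states an expectation held at entry, for New Subjects only. A dose can be expected to stay stable at enrolment and be adjusted later. The wordings sit badly together and should be reconciled, but the analysis gap does not depend on this.
- **That the bias is known to favour study drug and to grow with time.** Adjustment covers decreases too, and no passage says who receives increases or how often. The mix of subjects still observed also changes as subjects leave.

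**Conclusion.** The point holds as a limit on interpretation. The protocol permits ADT changes for therapeutic effect over 52 weeks, the SAP's efficacy summaries ignore them, and there is no comparator. Improvement after an ADT increase is therefore counted within the reported treatment effect.

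The direction is likely to favour ALKS 5461 if increases predominate, as the stated purpose of adjustment suggests. The size is unknown. The ranges of 0.1 to 1.8 MADRS-10 points and 0.5 to 9 percentage points of remission rest wholly on assumed shares and gains, and the low ends are negligible. It would be wrong to infer that the efficacy results are shown to be inflated by any given amount.

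No hypothesis test or error rate is involved, and the safety objective and the enrolment target of about 1,500 are untouched. This is a cheap improvement to an exploratory section.

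**What to change.** In SAP 3.5 and 3.6.2:

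- **(a) Tabulate ADT dose changes.** By visit, give the number (%) of subjects with an ADT dose increase so far and, separately, with a decrease. Add the time to first increase. Show both by prior-exposure group and overall.
- **(b) Add supportive response and remission rates.** At each visit and at the last assessment, count a subject as not achieved from the first ADT increase onward, with the same denominator as the main table. Keep the existing summaries.
- **(c) Continuous scores.** Do not use by-visit means restricted to scores before an increase as the correction for MADRS, HAM-A or CGI-S change. If these scores are explored, show observed means side by side for subjects with and without an ADT increase, labelled descriptive.

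Separately, the sponsor should reconcile the criterion 10 wording with the dose-adjustment passages in the synopsis, 8.4.2.1 and 9.5. No position is taken on which should stand.

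The cost is SAP wording and one extra table set from medication data already collected. The downside is that the supportive response and remission rates are conservative and must be labelled so.
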